9.3.3 Removal of Subjects from Therapy or Assessment

The investigator may discontinue study drug or withdraw the subject from the study at any time for safety or administrative reasons. The subject may decide to stop study drug or withdraw from the study at any time for any reason.

Subjects who discontinue taking study drug prematurely for any reason will undergo an ED Visit within 7 days of their last dose of study drug (see [Section 9.1.2.2](#)). Follow-Up Visits will also be scheduled 4 and 12 weeks after the last dose of study drug (see [Section 9.1.2.3](#)). Subjects who discontinue study drug prematurely will also be scheduled to return to the study site for each scheduled visit when clinical efficacy assessments are to be conducted (ie, at Visits 11, 14, 15, 16, 17, and 18, if these visits have not already been performed). At these visits, only clinical efficacy assessments (MMSE, CDR, ADAS-cog₁₄, FAQ, CBB and ISLT) will be conducted. Regularly scheduled clinical efficacy visits do not need to be attended if they fall within 8 days (visit window) after the Early Discontinuation Visit or within ± 8 days of either of the Follow-Up Visits (Visit 19 and Visit 20). Subjects who discontinue early from study drug are considered on study as long as they return for their regularly scheduled clinical efficacy visits as outlined above.

The primary reason for discontinuation and all other reason(s) contributing to the subject's discontinuation from study drug(s) should be collected on the Subject Disposition eCRF page. In addition, the date of last dose of study drug(s) will be recorded on the Study Drug Dosing eCRF page. If a subject discontinues study drug and withdraws from the study at the same time, the ED Visit will be followed (see [Section 9.5.5](#)).

Safety-related criteria for discontinuation of study drug include the following:

- a. A study drug discontinuation threshold will be set based on absolute counts of CD4 (T helper cells), CD8 (cytotoxic T cells), or CD19 (B cells). The discontinuation threshold will be set at below the level of the LLN, at a level that represents a greater risk of opportunistic infection in the treated population. For CD4 (T helper cells) the discontinuation threshold is 250 cells/ μ L. For CD8 (cytotoxic T cells) and CD19 (B cells) the discontinuation thresholds are 150 cells/ μ L and 50 cells/ μ L, respectively. Any subject who has CD4 (T helper cells), CD8 (cytotoxic T cells), or CD19 (B cells) absolute counts below the discontinuation threshold as confirmed by a repeat test conducted within 1 week of the initial test will be discontinued from study drug.
- b. Subjects with CD4 (T helper cells), CD8 (cytotoxic T cells), or CD19 (B cells) absolute counts between the LLN and the discontinuation threshold will have lymphocyte subset counts performed on a weekly basis. Subjects with a >33% reduction from baseline in CD4 (T helper cells), CD8 (cytotoxic T cells), or CD19 (B cells) absolute counts will also have lymphocyte subset counts performed on a weekly basis. For these subjects, the decision as to whether the subject remains on study drug or is to be discontinued from study drug will be based upon clinical judgment and will take into account any clinical presentation in addition to the lymphocyte subset counts. These subjects may continue with treatment if there is no clinical evidence of infection. They will be discontinued from study drug if they have infections of a moderate to severe intensity (eg, subjects whose infections are not localized, or are systemically unwell, or who require systemic anti-infective drug treatment).

Table 1 Study Drug Actions for Lymphocyte Subset Absolute Counts

| Lymphocyte subset absolute counts | Action | Decision to continue or discontinue |
|--|---|---|
| CD4 (T helper cells), CD8 (cytotoxic T cells), or CD19 (B cells) absolute counts below discontinuation threshold | Retest within 1 week | If retest performed within 1 week confirms lymphocyte subset counts below the discontinuation threshold, discontinue study drug |
| CD4 (T helper cells), CD8 (cytotoxic T cells), or CD19 (B cells) absolute counts between LLN and discontinuation threshold or >33% reduction from baseline in CD4 (T helper cells), CD8 (cytotoxic T cells), or CD19 (B cells) absolute counts | Lymphocyte subset counts to be performed weekly until counts return to \geq LLN or no more than 33% reduction from baseline | Decision will be based upon lymphocyte subset counts and clinical judgment |

LLN = lower limit of normal.

- c. Subjects with clinical evidence of infection will have their CD4 (T helper cells), CD8 (cytotoxic T cells), and CD19 (B cells) absolute counts measured. Blood and other biological samples will also be collected for investigations of infective pathogens (eg, serological tests, quantitative polymerase chain reaction, microscopy, and culture) where appropriate. In subjects with infection, if any of their absolute cell counts meets the discontinuation thresholds, study drug will be discontinued. All subjects with severe infections will be discontinued from study drug. All subjects with herpes zoster (shingles) or ocular herpes infections will be discontinued from study drug, regardless of severity of presentation. Subjects with mild or moderate infection may continue

treatment with study drug unless otherwise clinically indicated or otherwise specified below. Specifically, when any of the CD4 (T helper cells), CD8 (cytotoxic T cells), and CD19 (B cells) absolute counts are between the LLN and the discontinuation thresholds or have shown >33% reduction from baseline, subjects with infections of moderate intensity will be discontinued from study drug (eg, subjects whose infections are not localized, or subjects who are systemically unwell, or who require systemic anti-infective drug treatment). All subjects with infection who are discontinued from study drug will be followed for a period of 12 weeks or until the infection resolves/ stabilizes or until the CD4 (T helper cells), CD8 (cytotoxic T cells), and CD19 (B cells) absolute counts have returned to >LLN (whichever comes latest).

Table 2 Study Drug Actions for Lymphocyte Subset Absolute Counts and Infection

| Criterion | Severity of Infection | | |
|--|--|--|------------------------|
| | Mild | Moderate | Severe |
| CD4 (T helper cells), CD8 (cytotoxic T cells), or CD19 (B cells) absolute counts below discontinuation threshold | Discontinue study drug | Discontinue study drug | Discontinue study drug |
| CD4 (T helper cells), CD8 (cytotoxic T cells), or CD19 (B cells) absolute counts between LLN and discontinuation threshold or >33% reduction from baseline in CD4 (T helper cells), CD8 (cytotoxic T cells), or CD19 (B cells) absolute counts | May continue treatment with study drug unless clinically indicated | Discontinue study drug | Discontinue study drug |
| CD4 (T helper cells), CD8 (cytotoxic T cells), or CD19 (B cells) absolute counts always >LLN and no reduction from baseline >33% | May continue treatment with study drug unless clinically indicated | May continue treatment with study drug unless clinically indicated (See (e) for exception) | Discontinue study drug |

LLN = lower limit of normal.

- d. A subject with any skin rash of moderate to severe intensity, or any rash lasting more than 72 hours regardless of severity (see (e) for exception), will be discontinued from study drug and a dermatological consult will be requested regardless of whether the rash is considered drug-related or due to other causes. For cases where the investigator suspects a drug rash, regardless of severity, the subject will be discontinued from study drug, a dermatological consult will be requested, and a skin biopsy will be performed to confirm the diagnosis. The skin rash will be treated as per standard care and will be followed up until resolution regardless of etiology or severity.
- e. Subjects who develop moderate to severe oral or genital herpes should be discontinued from study drug. Subjects who develop a mild case of oral or genital herpes may remain on study drug even if the event lasts more than 72 hours.
- f. Development of any of the following features on MRI: vasogenic edema, macrohemorrhage, an area of superficial siderosis, or a symptomatic microhemorrhage. If discontinued from study drug, subjects will undergo an ED Visit within 7 days after discontinuation and will attend the Follow-Up Visits 4 and 12 weeks after the last dose of study drug. They will also undertake an Unscheduled Visit (with MRI) at approximately 4 weeks after the visit at which such MRI features were first identified. An MRI will also

be performed at approximately the time of the second Follow-Up Visit (Visit 20). Additional visits for safety may be arranged if clinically indicated in the opinion of the investigator, including after 12 weeks after the last dose of study drug. At any time during the treatment period, subjects who have asymptomatic, treatment-emergent microhemorrhages as detected by MRI, but none of the features which merit discontinuation of treatment (ie, vasogenic edema, macrohemorrhage, an area of superficial siderosis, or a symptomatic treatment-emergent microhemorrhage) may continue with treatment. These subjects will have safety assessments (including MRI) at approximately 4 weeks after the visit at which such MRI features were found. They will also continue with the scheduled MRI scans. Additional unscheduled MRI scans may be arranged on an individual subject basis in discussion with the study medical monitor.

- g. A postdose ECG with an average QTcF interval >500 msec from triplicate ECGs
- h. A postdose ECG with a QTcF interval increase from baseline >60 msec and a QTcF interval >450 msec as demonstrated from triplicate ECGs
- i. Any seizure (motor or non-motor)
- j. Pregnancy

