10. Subjects with hepatic impairment, with total bilirubin greater than 1.5 \times upper limit of normal (ULN) or International Normalized Ratio (INR) greater than 1.7 at Screening or Baseline. Subjects with Gilbert's syndrome need not be excluded.
11. Any contraindications to MRI or PET scanning, including cardiac pacemaker/ defibrillator or ferromagnetic metal implants (eg, in skull; cardiac devices other than those approved as safe for use in MRI scanners). Subjects who require sedation for MRI or PET scanning as per local guidelines need not be excluded.
12. Any contraindications to lumbar puncture (LP) for CSF sampling (eg, lower spinal malformation on physical examination, local spinal infection or other abnormality, including but not limited to obesity)
13. Severe visual or hearing impairment that would prevent the subject from performing psychometric tests accurately
14. History of Ig deficiency or other immunodeficiency disorders (including subjects known to be human immunodeficiency virus positive)
15. Subjects with chronic viral hepatitis
16. A history of tuberculosis (TB). Subjects with no history of TB will be tested for previous TB exposure (eg, positive tuberculin skin test, interferon gamma release assay or other locally accepted tests) and a positive test will be exclusionary.
17. A history of ophthalmic shingles
18. A history of ocular herpes simplex virus (HSV) infection

19. Any live vaccine in the 3 months before randomization.
20. Any active infection within the last 4 weeks prior to randomization. For such cases, the timing of randomization can be extended (up to 4 weeks) to allow the infection to resolve; psychometric tests conducted at Visit 2 (eg, MMSE, CDR) must be repeated.
21. Any chronic inflammatory disease that is not adequately controlled or that requires systemic or ocular immunosuppressive or immunomodulatory therapy. Subjects with:
 - a. Seasonal or perennial allergic rhinitis, asthma or chronic obstructive pulmonary disease where the condition is considered to be stable and adequately controlled by inhaled steroids need not be excluded.
 - b. Hashimoto's thyroiditis but who are stable on thyroid replacement therapy and not on systemic immunosuppressive therapy need not be excluded.
 - c. Cutaneous manifestations of immunological disease that do not require systemic immunosuppressive therapy or systemic immunomodulatory therapy need not be excluded (topical steroid treatment is permitted).

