9.5.1.5.2 SERIOUS ADVERSE EVENTS AND EVENTS ASSOCIATED WITH SPECIAL SITUATIONS

An SAE is any untoward medical occurrence that at any dose:

- Results in death
- Is life-threatening (ie, the subject was at immediate risk of death from the AE as it occurred; this does not include an event that, had it occurred in a more severe form or was allowed to continue, might have caused death)
- Requires inpatient hospitalization or prolongation of existing hospitalization
- Results in persistent or significant disability/incapacity
- Is a congenital anomaly/birth defect (in the child of a subject who was exposed to the study drug)

Other important medical events that may not be immediately life-threatening or result in death or hospitalization but, when based on appropriate medical judgment, may jeopardize the subject or may require intervention to prevent one of the outcomes in the definition of SAE listed above should also be considered SAEs. Medical and scientific judgment should be exercised in deciding whether expedited reporting is appropriate in such situations.

For this study, the following events should always be considered serious and reportable using the criteria of important medical event if the event does not meet other serious criteria: new onset seizures, ocular herpes.

In addition to the above, events associated with special situations include pregnancy or exposure to study drug through breastfeeding; AEs associated with study drug overdose, misuse, abuse, or medication error. These events associated with special situations are to be captured using the SAE procedures but are to be considered as SAEs only if they meet one of the above criteria. All AEs associated with special situations are to be reported on the eCRF whether or not they meet the criteria for SAEs.

All SAEs must be followed to resolution or, if resolution is unlikely, to stabilization.

The following hospitalizations are not considered to be SAEs because there is no “AE” (ie, there is no untoward medical occurrence) associated with the hospitalization:

- Hospitalizations for respite care
- Planned hospitalizations required by the protocol
- Hospitalization planned before informed consent (where the condition requiring the hospitalization has not changed after study drug administration)

- Hospitalization for administration of study drug or insertion of access for administration of study drug

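### In Version 3.0, Table 2 of 9.3.3 allows study drug to continue in three cells without excepting herpes zoster or ocular herpes, which item (c) stops at any severity

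*Protocol*

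**What the plan says.** Protocol 9.3.3 lists the safety criteria for stopping study drug as items (a) to (j). Item (c) deals with infection and is unconditional for two kinds: "All subjects with herpes zoster (shingles) or ocular herpes infections will be discontinued from study drug, regardless of severity of presentation". The next sentence lets subjects with mild or moderate infection continue "treatment with study drug unless otherwise clinically indicated or otherwise specified below".

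Table 2 follows item (c). It crosses three lymphocyte-count bands with three severities of infection and gives an action in each cell. Most cells stop study drug, but three are permissive. The one for normal counts with moderate infection reads "May continue treatment with study drug unless clinically indicated (See (e) for exception". The other two, for mild infection with intermediate and with normal counts, use the same permissive wording without the cross-reference.

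Item (e), to which that cross-reference leads, begins "Subjects who develop moderate to severe oral or genital herpes should be discontinued from study drug" and then lets mild oral or genital herpes stay on drug. Item (d) is a separate rule on rash: a rash of moderate to severe intensity stops study drug, and "any rash lasting more than 72 hours regardless of severity (see (e) for exception), will be discontinued from study drug".

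**The concern.** The text makes zoster and ocular herpes a mandatory stop, while the table for the same item makes it optional in three situations. A site that works from the table could treat the decision as one of clinical judgment. That changes what happens to the subject: 9.4.1 allows dosing to be suspended for a concurrent illness and later resumed after discussion with the medical monitor, whereas under 9.5.5 a subject who has discontinued may not restart. A subject whom item (c) takes off drug for good could therefore be paused and resumed.

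The protocol itself treats these infections as special. Section 9.5.1.5.2 names as always serious "new onset seizures, ocular herpes". The exclusion criteria in 9.3.2 include "A history of ocular herpes simplex virus (HSV) infection" and "A history of ophthalmic shingles". Section 9.2.6 counts shingles among the discontinuation criteria meant to reduce clinical risk.

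**Working it through.** No formula applies. The check sets the printed action in each cell of Table 2 beside what item (c) requires for zoster or ocular herpes.

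| Count band | Mild: table / (c) | Moderate: table / (c) | Severe: table / (c) |
|---|---|---|---|
| Any count below the discontinuation threshold | stop / stop | stop / stop | stop / stop |
| Intermediate: between LLN and threshold, or a fall of more than 33% | may continue / stop | stop / stop | stop / stop |
| Normal: above LLN and no fall of more than 33% | may continue / stop | may continue, pointer to (e) / stop | stop / stop |

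1. Cells: 3 bands × 3 severities = 9.
2. Cells where the table stops: 3 + 2 + 1 = 6. Item (c) stops in all 9 for these two infections. Cells in conflict: 9 − 6 = 3.
3. Exceptions in those 3 cells: one has a pointer, to (e). Item (e) names oral and genital herpes only, so none of the 3 leads to the zoster and ocular herpes rule. The table's only note explains an abbreviation.
4. Item (c)'s general permission does not close the gap. Its carve-out refers to what is specified below, whereas the zoster and ocular herpes rule stands in the sentence above it.
5. Oral and genital herpes: (e) stops moderate and severe cases, and the normal/moderate cell points there. Mild cases may stay on drug, as the permissive mild cells say. There is no conflict for these infections.
6. Other stop rules that could apply in the 3 cells: (d) applies when there is a skin rash that is moderate to severe or lasts beyond 72 hours. For ocular herpes without a skin rash, nothing in 9.3.3 other than (c) stops study drug in these cells on account of the infection.
7. Reporting rules: 9.5.1.5.1 requires a herpes zoster infection to be described in detail to the Medical Monitor. Ocular herpes is always serious under 9.5.1.5.2 and, under 9.5.4.1, must be reported within 24 hours of the investigator becoming aware of it. Neither rule itself stops study drug.

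**The case against.** The strongest reply is that the table omits a rule but does not contradict it. Its wording is permissive and leaves room for clinical judgment, so a site that stops a zoster case under (c) breaches no cell. The grid has no axis for type of infection, the items of 9.3.3 apply side by side, and the table does not restate the seizure rule either, yet nobody would read it as overriding that rule. Item (c) stands immediately before the table, and both infections come to the sponsor's attention through reporting.

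Much of this stands, and it keeps the point small. It does not remove it. This is the action table for infection, zoster and ocular herpes are infections, and a permission there is at odds with a rule that leaves no discretion. The table also flags one exception, so a reader may reasonably take the exceptions as complete.

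A further reply is that (b) and (c) give infections needing systemic anti-infective treatment as examples of moderate or worse intensity, so a case on systemic antivirals would not be mild. That takes such cases out of the two mild cells. With normal counts, however, it moves them into the moderate cell, which is also permissive.

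Two stronger readings are tempting. A reader might infer that the table instructs sites to keep dosing, or that many subjects would stay on drug in error. The cells only permit continuation, and the protocol gives no rates for these infections. A reader might also infer that the protocol now in force carries the conflict. This copy of 9.3.3 is the Version 3.0 (Amendment 01) text. Another copy of Appendix 2 bears Amendment 02 marks, so a later version exists, and its 9.3.3 is not shown.

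**Conclusion.** Wrong as written in Version 3.0, with low severity: a safety conflict between text and table that could usefully be corrected. For herpes zoster and ocular herpes, 3 of 9 cells of Table 2 permit what item (c) forbids. That is a count of cells, not a measure of risk; the cells have no known weights.

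The risk is limited by the explicit rule directly above the table, by item (d) where there is a qualifying rash, and by the two reporting requirements. The exposure that remains is a site relying on the table alone, and it is least covered for ocular herpes without a skin rash. How far (d) reduces the conflict for zoster cannot be counted, because that would require assuming that rash severity equals infection severity, which the protocol does not say. No sample size, error rate or efficacy analysis is affected.

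**What to change.** If the current version still reads this way, mark the three permissive cells of Table 2 with one footnote: *Except herpes zoster (shingles) and ocular herpes, which always stop study drug under 9.3.3(c); oral or genital herpes follows 9.3.3(e).* This brings the conflicting cells from 3 to 0. Item (c), the grading of adverse events and the other six cells stay as they are. The cost is one footnote and a line in site training.

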9.4 Treatments

9.4.1 Treatments Administered

For this study the test drug is E2609 and the control drug is placebo. All study drugs are to be administered orally, QD, with food.

Treatments to be administered in Stage A and Stage B are shown below and in [Figure 1](#). The 2 highest E2609 doses (15 mg and 50 mg) taken into Stage B, after the PK/PD and safety review from Stage A, will be used for the mild to moderate AD population in Stage B. (revised per Amendment 01)

- Stage A: 3 doses (5 mg, 15 mg, and 50 mg) of E2609 or placebo
- Stage B, MCI/Prodromal Cohort: 3 doses (5 mg, 15 mg, and 50 mg) of E2609 or placebo
- Stage B, Mild to Moderate AD Cohort: 2 doses (15 mg and 50 mg) of E2609 or placebo. (revised per Amendment 01)

Study treatment will begin on Day 1 (at the study site) following Randomization and will continue for approximately 78 weeks. Please refer to [Table 7](#) and [Section 9.5.1.4.1](#) for specific information on drug administration on days when PK sampling is to be performed.

Study drug doses will remain the same for each individual subject unless the interim PK/PD analysis determines that an entire dose level requires adjustment ([Section 9.4.4](#)). See [Section 9.3.3](#) for safety-related discontinuation criteria of study drug. If a subject develops a concurrent illness during the treatment period, the investigator should discuss with the medical monitor on whether dosing with study drug needs to be temporarily suspended. As a general clinical guideline, dosing with study drug may be resumed after resolution or stabilization of the concurrent illness, after discussion with the medical monitor.

9.4.2 Identity of Investigational Product

E2609 tablets of 5-mg, 10-mg and 25-mg dose strengths will be supplied. Placebo tablets of identical appearance will also be available. Each subject will receive 2 tablets, which combined will make up the required doses of E2609 5 mg, E2609 15 mg, E2609 50 mg, or placebo. The tablets will be supplied by the Sponsor in labeled blister packs. The product release certificates for E2609 and placebo will be included in the clinical study report for this protocol.

Subjects will be stratified and randomized, and drug will be dispensed, via an interactive voice and web response system (IxRS) system (see [Section 9.4.3](#)).

The sponsor will provide the study drugs packaged in a double-blind configuration. Each subject's study tablets will consist of either E2609 or placebo, or both (see [Section 9.4.2.3](#) for labeling details).

